11.2 Unique participant ID

Each participant in IBBS has two codes, which helps to link the data and ensure data confidentiality. The codes do not contain personally identifiable information and cannot be used to identify an individual.

ID-code is assigned to each participant by coupon manager and is recorded in all source documents in IBBS. The ID-code consists of two-letter city code, and three-digit sequential number (0001-0010 for seeds, and 0011-0999 for other participants).

An additional QR code is used to link electronic forms in the PHC_research app. It has the same elements as the ID-code, with additional letters "PW" between the city code and sequential number. The QR-code is printed on the participant's coupon, and after scanning it with the PHC_research app, it is populated into linked forms: screening, questionnaire, medical testing, test results, primary compensation, coupon dissemination, secondary compensation.

Only the coupon manager is responsible for storing, maintaining, and assigning QR codes to participants. Access to the ID code link-log has a principal investigator, co-investigator, and national coordinator. ID code link-log will be stored on the "PHC-research" software server.

11.3 Data access

Only the Principal investigator and co-investigators will have access to the data and documents, the division of responsibilities between the personnel (primary data and coding, data entry, analysis, report preparation) will be ensured. Documents and computers will be password protected (at least one small letter, one capital letter, one digit and one character).

Roles are assigned to selected individuals to create analysis data sets to minimize redundancy. To ensure secure access to data, one-factor authentication for each role and a horizontal hierarchy of access to information are used. Each regional team member only has access to their block in «PHC_Research» software: screening, questionnaire, medical testing, test results, primary

compensation, coupon dissemination, secondary compensation. Each block is accessed through verification with the help of a personal login and password, which each representative of the research team has.

«Screening» is completed by the coupon manager, and after filling becomes inactive for editing.

«Questionnaire» is filled out by the interviewer during the face-to-face interview. Changes to the Questionnaire block are possible after filling in. Changes are made if the respondent decides to change his / her answer to the questionnaire and informs the interviewer after the interview is completed.

«Medical testing» is completed by a healthcare worker, recording the fact of providing consultation and testing to each IBBS participant. The block after filling becomes inactive for editing.

«Test result» is completed by the healthcare worker at the end of each day. This block contains information from the Test Results Form that the healthcare worker fill throughout the day for each study participant.

«Primary compensation» is filled in by the coupon manager, which records confirmation that the respondent has been compensated for his participation. The block after filling becomes inactive for editing.

«Coupon dissemination» is filled in by the coupon manager, which to capture the codes of issued coupons to recruit other PWID if the participant has agreed to become a recruiter. The block after filling becomes inactive for editing.

«Secondary compensation» is filled in by the coupon manager, which records the fact of payment to the participant after recruiting others PWID.

Principal investigator will have direct access to the data on the server. To ensure secure access to data, double authentication is used for the principal investigator. The administrator of PHC Information Systems Support Division has access via RDP / SSH to the system and its settings, without access to the research data.

Researcher access to data is traceable and to prevent sharing of access credentials. A full audit will be performed through the web interface (user login identification). Email is not used to transfer data through software.

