7.0 PROCEDURES

7.1 Participant algorithm

Each participant will have to complete four stages of the survey; the approximate total duration to complete all steps is 82-195 minutes:

Completion of each stage has to be verified by the responsible staff in the Participants' Card (Annex 10. Participant's Card).

Stage:	STAGE 1. SCREENING			STAGE 2. BEHAVIORAL COMPONENT	
	Screening of potential participant	Coupon validation	Informed consent signing	Survey	
Responsible staff:	Coupon-manager Healthcare professional	Coupon-manager	Participant, involving coupon-manager	Interviewer	
Approximate duration:	5 minutes	1 minute	10-15 minutes	30-40 minutes	

Stage:	STAGE 3. BIOLOGICAL COMPONENT							
	Pre-test counseling	Capillary blood collection with EDTA k3 blood micro containers	Testing for HIV, hepatitis C, syphilis (rapid tests)	Second HIV rapid diagnostic test for those with first positive test	Third HIV rapid test for those, who are positive for first and second rapid tests	Blood collection for DBS to test the recent HIV-infection and viral load (for HIV-positives and those who stated that they are receiving ART)	Notifying participants of their testing results	Referral to HIV clinics (for HIV-positives) / Referral to HCF (for other)
Responsible staff:	Healthcare professional	Healthcare professional	Healthcare professional	Healthcare professional	Healthcare professional	Healthcare professional	Healthcare professional	Healthcare professional
Approximate duration:	5-10 minutes	5 minutes	10-15 minutes	10-20 minutes	10-20 minutes	3 minutes	10-20 minutes	5 minutes

Stage:	STAGE 4. COMPENSATION AND PEER RECRUITMENT				
	Primary compensation (participant)	Other PWID recruiting instruction	Other PWID recruitment	Other PWID participation in the survey	Secondary compensation (recruiter)
Responsible staff:	Coupon-manager	Coupon-manager	Participant	Participant	Coupon-manager
Approximate duration:	1 minute	5 minutes	up to 20 days	82-195 minutes	1 minute

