8.1 Pre-test counseling

After completing the survey and before capillary blood collection, all participants undergo a pre-test counseling on HIV in accordance with the National Protocol on HIV testing services. Pre-test counseling includes clarification of the ways of contraction and transmission of HIV infection, HCV and syphilis, the significance of test results, the risks associated with injection drug use and risky sexual behavior, as well as prevention and treatment of HIV and sexually transmitted infections.

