8.8 Post-test counseling and referral to services

HIV: All respondents undergo post-test counseling in accordance with the National Protocol of the HTS. The participants with HIV-positive result under the second and the third rapid diagnostic tests are informed by healthcare workers about the final result (Annex 17. Certificate of HIV test results) and referred on the same day to the nearest HIV clinic or ART site for ART initiation (Annex 16. Referral form for the survey participant; Annex 20. Registration log for referrals to HIV Clinics). During the data collection phase, representatives of local NGOs providing HIV testing and linkage services to PWID will be present at survey sites, and will enroll newly detected HIV positive participants in their projects, which provide active referral (accompanying) to HIV clinics and extended follow-up. The regional coordinator ensures the presence of social workers from a specialized NGO on the study site to accompany participants. If one social worker will not be enough, the regional coordinator will attract the necessary number of specialists to the site. Additionally, information on the referral to medical institutions, including the HIV clinic, is indicated in the informed consent that is provided to participant when he/she arrives at the site.

In accordance with the national procedure of ART prescription (Order of the Ministry of Health of Ukraine No. 551 of 2010), ART can be initiated immediately after an HIV-positive representative of a key groups is linked to care. The reluctance of HIV-positive participants to be registered with a HCF may be an obstacle to starting treatment the same day. Therefore, the specialized projects provide extended follow-up to ensure linkage to care when participant is ready for this.

If present in the city, additional referrals will be provided to social care and support projects (Annex 19. Social support referral form for the survey participant).

In case of HIV negative result all PWID who tested negative will be informed about PrEP options, which are available for free at the nearest HIV clinic/ART site. They will be offered to be accompanied by the social worker for PrEP initiation.

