9.6 Treatment cascade indicators among PWID living with HIV

HIV treatment cascade calculation will include the following indicators:

Cascade indicator	Calculation
PWID living with HIV	The latest available PWID population size estimate will be multiplied by the prevalence of HIV among PWID according to the IBBS 2023 data
Know about their HIV-positive status	The proportion of PWID who self-reported their HIV-positive status during survey (among those who received HIV-positive rapid test result upon survey and agreed to answer questions about their experience of previous HIV-testing). This calculation will be cross-checked with the healthcare worker's forms.
Registered in the HIV clinic	The proportion of PWID who self-reported to be officially registered in the HIV clinic as HIV-positive (among those who received HIV-positive rapid test result upon survey and agreed to answer questions about their experience of previous HIV-testing). This calculation will be checked through the healthcare worker's form.
Receive ART	The proportion of PWID who self-reported receiving ART (among those who received HIV-positive rapid test result upon survey and agreed to answer questions about their experience of previous HIV-testing).

¹³ Dumchev, K., Sazonova, Y., Salyuk, T., & Varetska, O. (2018). Trends in HIV prevalence among people injecting drugs, men having sex with men, and female sex workers in Ukraine. *Int J STD AIDS*, 29(13), 1337-1344.
doi:10.1177/0956462418784096

¹⁴ Kassanjee R, McWalter TA, Bärnighausen T, Welte A. A new general biomarker-based incidence estimator. *Epidemiology*. 2012 Sep;23(5):721-8. doi: 10.1097/EDE.0b013e3182576c07.

	testing). This calculation will be checked through the healthcare worker's form.
HIV viral suppression	Results of viral load testing carried out at the stage of laboratory analysis.

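### The questionnaire can be edited after the HIV result is disclosed, and no stated rule keeps the pre-result answer for the awareness step

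*Protocol*

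**What the plan says.** Section 11.3 describes the data blocks in the PHC_Research software. Of the interview record it says "Changes to the Questionnaire block are possible after filling in", and it gives the trigger: "Changes are made if the respondent decides to change his / her answer to the questionnaire and informs the interviewer after the interview is completed". It sets no time limit, no list of items that may not be changed, and no link to the moment at which test results are given. Other blocks are treated differently; for example, "Screening» is completed by the coupon manager, and after filling becomes inactive for editing".

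Sections 7.1 and 8.1 fix the order of the visit. The interview is stage 2 and the biological component is stage 3: "After completing the survey and before capillary blood collection, all participants undergo a pre-test counseling on HIV". Stage 3 includes a step headed "Notifying participants of their testing results". Under section 8.8, participants with a confirmed positive result are "referred on the same day to the nearest HIV clinic or ART site for ART initiation".

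Section 9.6 defines awareness as "The proportion of PWID who self-reported their HIV-positive status during survey", and the ART step begins "The proportion of PWID who self-reported receiving ART". Both are taken among those positive on the survey's own rapid test who agreed to answer about previous HIV testing. Both are to be checked against the healthcare worker's form.

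**The concern.** Awareness is meant to capture what HIV-positive participants knew when they arrived. Holding the interview before the test is what gives self-report that meaning. An edit rule with no cut-off weakens this protection: once told the result, a participant can ask the interviewer to change an answer from negative or unknown to positive. If the changed answer is analysed, awareness created by the survey's own test counts as prior awareness.

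Awareness feeds the 95-95-95 monitoring described in section 13.1, and knowledge of status is part of the HIV testing indicator in section 13.2. Knowledge of transmission routes is a separate objective (section 3.0). Pre-test counselling explains those routes (section 8.1), so knowledge answers become open to change even earlier, when stage 3 starts.

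**Working it through.** The plan gives no figure for this point, so there is none to reproduce. The check sets the sections side by side and then gives an illustration of size.

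**1. Which blocks lock (section 11.3)**

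| Block | Stated rule |
|---|---|
| Screening | locks on completion |
| Questionnaire | can be changed at the respondent's request |
| Medical testing | locks on completion |
| Test result | no lock stated |
| Primary compensation | locks on completion |
| Coupon dissemination | locks on completion |
| Secondary compensation | no lock stated |

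Four blocks lock, two are silent, and only the Questionnaire is expressly left open.

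**2. Whether an edit can follow disclosure.** The interview is stage 2, disclosure is in stage 3 and compensation is stage 4 (section 7.1). The participant is still on site after hearing the result, and may return for secondary compensation (section 7.5). The permitted edit window therefore includes the time after disclosure.

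**3. Whether the definition excludes such edits.** Section 9.6 places the self-report within the survey. It does not say before the result, and it does not say which answer is used if there are two.

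**4. What the safeguards do**

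- Cross-check with the healthcare worker's forms (9.6): no rule is given for discordant records. Section 11.3 says that the Medical testing block records that counselling and testing took place. Nothing says that these forms capture status known before the result.
- Individual interviewer logins (7.4) and an audit by user login (11.3): these identify users. Keeping the original answer and the time of the edit is not stated.
- Daily backup after midnight (11.4): an edit made on the day of the visit precedes it.

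**5. Illustration of size.** Let a be the true share of test-positives who already knew their status, and u the share of the previously unaware whose answer is changed after disclosure. The protocol gives neither, so both are assumptions. Also assumed are 629 HIV-positive participants (section 4.4), and that the planning design effect of 3.0 (section 4.4) applies to awareness.

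- Upward bias = (1 − a) × u
- 95% half-width = 1.96 × √(3.0 × a(1 − a) / 629)

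Example with a = 0.7 and u = 5%: the bias is 0.3 × 0.05 = 1.5 points, or about 9 of 629 people. The half-width is 1.96 × √(0.63 / 629) = 6.2 points.

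| a | Bias, u = 1% | u = 5% | u = 10% | u = 25% | Half-width | u at which bias equals half-width |
|---|---|---|---|---|---|---|
| 0.9 | 0.1 | 0.5 | 1.0 | 2.5 | 4.1 | 4.06 / 10 = 41% |
| 0.7 | 0.3 | 1.5 | 3.0 | 7.5 | 6.2 | 6.20 / 30 = 21% |
| 0.5 | 0.5 | 2.5 | 5.0 | 12.5 | 6.8 | 6.77 / 50 = 14% |

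Bias and half-width are in percentage points. The bias exceeds sampling error only where edits after disclosure are frequent and prior awareness is low. Unlike sampling error, it would not shrink in a larger sample.

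**The case against.** The other side has a good deal to say.

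- The default answers are taken before testing. An edit needs a request from the respondent and action by the interviewer. Team members can open only their own block, so the healthcare worker who gives the result cannot change the questionnaire. Compensation does not depend on the answers. A reader might infer that the cascade is contaminated; the protocol shows only an unguarded possibility. This stands.
- A reader might infer that the original answer is overwritten and the edited one analysed. The protocol says neither. It also does not say that the original is kept, so the gap remains.
- The direction is not fixed. A late edit may reveal a known status or current treatment that was withheld at interview, and so make the estimate more accurate. This stands, and it is a reason to keep both answers rather than forbid corrections.
- A reader might infer that the ART step is as exposed as awareness. It is not: someone diagnosed that day is only being referred to start ART and has little reason to report receiving it. The likelier ART edit is a late admission of real treatment.
- If the items ask about testing before the survey, a new result does not change the truthful answer. The questionnaire is not shown, so this cannot be settled.
- The standard operating procedures listed in section 12.1 may set a cut-off, and an analysis plan may name the answer used. Either would help. The protocol's own text nevertheless states an open edit rule, and a later choice of answer works only if the original has been kept.

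**Conclusion.** The point holds as a gap in data capture. Section 11.3 permits the answer behind the awareness step to be changed after the result is known, and no stated safeguard secures the pre-result answer. Awareness is the step mainly at risk. HIV-knowledge items are exposed from the start of counselling, and ART only slightly.

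The size is unknown because the protocol gives no rate of edits. On the assumptions above, the upward bias is at most 2.5 points when 5% or fewer of the previously unaware edit, which is probably small beside sampling error. It could exceed sampling error only at high edit rates combined with low prior awareness. Corrections of earlier non-disclosure would act as genuine improvements and are not counted in that range. This is a cheap improvement to make before fieldwork, not evidence that the cascade estimates will be wrong.

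**What to change.** **Section 11.3.** Lock at least the HIV-testing, status, registration, ART and HIV-knowledge items before stage 3 begins, that is, before pre-test counselling. Record any later correction as a separate, time-stamped entry that leaves the original answer in place.

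**Section 9.6.** State that awareness, registration and ART use the pre-result answer, and that later corrections enter only a sensitivity analysis. Add a rule for records that disagree with the healthcare worker's form.

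**Cost.** A lock setting of the kind the software already applies to four blocks, one additional entry field, and a few sentences of text. The downside is that genuine late corrections need a separate entry and do not enter the main estimate; the sensitivity analysis shows how much they matter.

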11.4 Data security

From paper forms, data will be transferred to electronic format by a team member who do not have access to participants and will be involved only at the stage of entering information into the dataset. Each of these specialists will sign the Data Use and Confidentiality Agreement, which minimizes the risk of incorrect use of information. All reporting forms of regional teams will be checked by the Principal investigator and aggregated by him.

The regional coordinator is responsible for storing documents in a safe or locked cabinet, which will be located in his office. During the field stage, the regional coordinator will report on recruiting and the main results of the sampling every week, which will quickly receive information (if any of the documents are lost, it will be possible to restore files inclusively until the current week). The regional coordinator will immediately inform the Principal investigator of any unplanned situation with paper

forms in order to receive information on further steps. If some paper documents are lost or something happens to them, the Principal investigator will have access to the data array and will be able to recover the information (the data array will be filled online through «PHC_Research»).

Data transfers done through secure methods, and data are encrypted before transfer. Data transfer protection guaranteed by SSL/TLS 1.3 with Advanced Encryption Standard 256. To protect data that is entered through «PHC_Research», a cryptographic library for mobile devices is used. To develop the application, the most protected Android SDK Java Development Technology tool will be used.

An array of survey data and accompanying documents will be stored on a cloud protected server of the PHC, unavailable through the common networks. Database security is controlled by a firewall on the PHC server, and all data is stored in encrypted form. The database will be protected against viruses and other malware. To do this, anti-virus software is used on the central database, server and user computers.

The PHC Information Systems Support Division will administer the server, which involves daily backups and emergency recovery in case of server failure. The backup system is based on the RAID 10 or 01 scheme. A full backup is planned once a day after midnight on a separate sector of the PHC server. All data is encrypted on both sectors - primary and backup.

As the main implementer and owner of the data, the PHC is responsible for data arrays storage for at least 10 years after the completion of the survey. Only the Principal investigator will have access to cross cutting shredders. As needed intermediate data will be securely destroyed. Such data will be deleted by the Principal investigator from his computer, access to which is ensured by a strong password (no other staff will have access to this computer).

All paper documents will be stored in a secure place, in a safe in the office of the Principal investigator. After the presentation of the final IBBS report, all documents will be transferred to the general PHC archive, access to which will be available only to the Principal investigator upon request. After 5 years after the completion of IBBS, paper forms will be destroyed by national team using a shredder in accordance with the general document management policy at the PHC.

The study does not involve the collection of interim data.

After the field stage has been completed all tablets will be formatted and reset to factory settings by a national team.

12.0 DATA QUALITY ASSURANCE

The implementer will employ a range of measures at all stages of survey to assure quality of data.

12.1 Preparatory stage

The Protocol and the SOPs will be reviewed and approved by the National IBBS Working Group. Standard operating procedures (SOPs) will be developed to provide a consistent algorithm for data collection at all sites of the IBBS. The SOPs will cover the following aspects of survey implementation:

- recruitment and screening;
- prevention of re-participation in the survey and exclusion of non-eligible participants;
- informed consent;
- confidentiality of participants;
- completion of the survey instruments;
- collection and testing of biological samples;
- pre- and post-test counseling, referrals to healthcare facilities;
- storage and transportation of dry blood spots;
- compensation to respondents for participation in the survey, recruiting of other participants;
- survey algorithm for participants;
- team work on the survey site, its activation and closure;
- confidentiality of the participants;
- securing survey site for participants and staff;
- arrangement of waiting room;
- data management on the survey site;
- weekly reporting;
- survey monitoring and data quality assurance.

The personnel training is carried out based on the Protocol and SOPs, and the availability and compliance with the documentation on the sites is checked during monitoring visits. The personnel (regional teams, healthcare workers, monitoring consultants) will undergo a specialized training.

